## ANALYSES AND STATISTICAL CONSIDERATIONS

Analysis of subjective ratings, plasma hormonal measures, Brunch Food Task, and diet 3-day food measures will be assessed using a mixed-model repeated measures analysis (PROC MIXED SAS V9.4, Cary, NC) to assess main effects and interactions for the fixed factors of obesity status (lean vs. obese) and time (before vs. after intervention), and subjects will be the random effect factor to accommodate correlation between repeated measures. Covariate adjustment will be included for age and sex.

Using these random effects models applied to whole brain analysis for neural responses and mixed effects models for other analyses, the following specific hypotheses will be tested for each aim:

Sample size estimates are based on effect size determinations from our preliminary work and related previous research. Based on Jastreboff et al (2016) findings from lean (n=14) vs. obese (n=24) adolescents, we found an overall large effect sizes between  $d=0.65$  and  $0.56$  for the mPFC responses in the lean and obese adolescent groups, and  $d=0.68$  and  $0.53$  for the striatal (caudate) response in the lean and obese adolescents as well as an effect size  $d=0.569$  for lean vs. obese for the PFC connectivity with the striatum. The described fMRI liraglutide study by Farr et al. (n=18) found effect size placebo=0.53 and liraglutide=-0.47 for decreased activation in the parietal cortex. There are no specific studies examining the effect of liraglutide on CBF response to HFCS ingestion. Based on these earlier studies, we will include 45 subjects in our study; specifically, 15 healthy lean and 30 obese adolescents to

test the proposed hypotheses.

For the adolescents, the goal is to have pilot data inclusive of adolescents with the food snack task alone – to obtain funding inclusive of adolescent age and add to literature. The effects of the medication on eating behavior are fairly robust which is why I believe we were able to see differences in initial pilot data. The main goal is to investigate the impact on eating behavior (assessed in the food snack task) before and after the medication (so baseline vs. post intervention). The lean participants serve as “controls” in that after the medication, the individuals with obesity have eating behavior more similar to that observed in lean. We also do within subject comparison (obesity before medication vs. after) - that is the main question.

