**TRIAL SUMMARY**

Abbreviated Title	Effect of liraglutide on neural responses to HFCS in individuals with obesity
Trial Phase	2A
Indication	Healthy lean (n=15) and obese individuals (n=30)
Control	N/A
Product	Liraglutide
Number of Subjects	45
Estimated Enrollment Period	24 months
Aims	Aim 1 – To investigate the effect of 12-16-week intervention with GLP-1 analogue (liraglutide 3.0mg) on eating behavior and food craving in individuals with obesity (age 15-39 yrs) who chronically consume SSBs ( $\geq$ 5 SSBs/week).
Inclusion Criteria	
 
1. 15-39 years old
 
2. Lean (BMI 18.5-24.9 kg/m^2) with normoglycemia with fasting plasma glucose (FPG) <100 mg/dL, 2-hour post oral glucose tolerance test (75gm glucose) glucose level <140 mg/dL and glycosylated hemoglobin (HbA1c) <5.7% or
 
3. Obese (BMI 30-45 kg/m^2) with or without prediabetes (insulin resistance) but without diabetes <200 mg/dL,
 
4. Ingest <math>\geq</math>5 sugar sweetened beverages per week,
 
5. Weight stable for at least 6 months,
 
6. Able to provide written and verbal informed consent,
 
7. Able to read and write in English Able to read and write in English,
 

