Exclusion Criteria	
 
1. Current active participation in a weight loss program or weight loss of <math>\geq</math>10% of total body weight during the previous 6 months,
 
2. Prior bariatric surgery or current gastric balloon,
 
3. Following a vegetarian/vegan diet or dieting/restricting food due to significant food allergies, including but not limited to lactose intolerance and celiac disease,
 
4. Significant medical condition such as cardiac or pulmonary disease, coagulopathy, gastrointestinal disorder, known history of Type 1 or T2D, current psychiatric disorders (including suicidal ideation and depression), including eating disorders (DSM-IV criteria), neurological injury or illness
 
5. Current use of weight-loss medications or supplements, psychiatric medications or anti-hyperglycemic medications (stable dose of metformin for <math>\geq</math> 6 months is acceptable),
 
6. History of or family history of multiple endocrine neoplasia type 2 (MEN-II) or medullary thyroid cancer, alcoholism, or previous history of pancreatitis,
 
7. Females who are pregnant or lactating, or who are unwilling to use proper contraception or remain abstinent,
 

Treatment Plan	Eligible obese subjects will self-administer Liraglutide once daily for 12-16 weeks.

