## STATEMENT OF PURPOSE/OBJECTIVES

**Aim 1** – To investigate the effect of GLP-1 analogue (liraglutide 3.0mg) on eating behavior and food craving in individuals with obesity (age 15-39 yrs) who chronically consume SSBs ( $\geq 5$  SSBs/week).

**Exploratory Aim:** To investigate the role of specific metabolic/hormonal responses (serum leptin, insulin, glucose, GLP-1, acyl-ghrelin) induced by food consumption, and in the setting of liraglutide treatment

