#### **Duration of Therapy**

For Obese patients, Liraglutide will be administered daily for 12-16 weeks. If any of the following occur, the medication will be stopped:

- Pancreatitis (severe abdominal pain, increased amylase/lipase)
- Severe dehydration
- The participant chooses not to continue in the study

Lean controls will not be given study drug.

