## Eating Behavior Assessments

To assess food preference and food intake before vs. after liraglutide intervention, eating behavior will be assessed in three ways;

**Lab-based Food Brunch Task:** At baseline and during the last week of treatment, each participant will undergo the food brunch task. Participants will be given the opportunity to eat ad libitum for 30 minutes with detailed measurement of food/drink consumed and video recording to assess eating topography. We will obtain signed permission prior to any video recording and the participant will know when they are being videotaped. The videotape recording will be used for research only. The recording will not be shown to the general public and will not be identified with the subject's name, although their face may be included in the recording. Declining to be videotaped will not affect the participant's study participation or

treatment in any way.

The food brunch task is adapted from [name] on the basis of previous work on exposure to food cues and foods in the laboratory, which indicates that sufficient quantities, multiple food options and sufficient time available for eating are important variables modulating food intake. In the food brunch task, participants will be presented with a choice of the following foods, presented in 6 discrete bowls: skittles, M&Ms, chips, pretzels, cookies and popcorn. They will be offered the food and drinks and allowed to eat and drink as much as they like for 30 minutes. Video recordings will be assessed for frequency of times each bowl is touched/reached for, frequency of pick-ups and number of bites taken. The type and amount (weight and kilocalories) of food/drink consumed by each subject will be assessed before and after each session. All remaining items will be weighed by trained staff in the Yale Center for Clinical Investigation Metabolic Kitchen.

The instructions will state: "There are different foods and drinks on the tray. We will leave these here for you and you can eat and drink as much or as little as you like during the next half hour". We will draw labs at the following time intervals during the food brunch task: 0, 15 and 30 minutes.

Participants will also be asked to complete the following questionnaires during each food snack test visit at 4 time points (baseline and then q 10 minute intervals): Hunger Scale, Anxiety Scale, DES-R and Food Craving Scale.

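### Aim 1 is worded as the effect of liraglutide, but its main contrast is an uncontrolled before/after change, and the documents conflict on whether lean participants repeat the food task

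*Combined protocol and SAP*

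**What the plan says.** **The aim.** The Trial Summary words Aim 1 as "To investigate the effect of 12-16-week intervention with GLP-1 analogue (liraglutide 3.0mg) on eating behavior and food craving in individuals with obesity". The Statement of Purpose/Objectives repeats it without the duration.

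**The design.** The Control row of the Trial Summary is marked not applicable. On treatment it says "Eligible obese subjects will self-administer Liraglutide once daily for 12-16 weeks". Under Duration of Therapy: "Lean controls will not be given study drug". There is no placebo, randomisation or untreated obese group.

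**The contrast.** Analyses and Statistical Considerations says "We also do within subject comparison (obesity before medication vs. after) - that is the main question". It describes the lean group as controls in the sense that, after treatment, "the individuals with obesity have eating behavior more similar to that observed in lean". The same section plans a mixed model with obesity status, time and their interactions as fixed factors, subject as a random effect, and adjustment for age and sex.

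**Who repeats the task.** Eating Behavior Assessments says "At baseline and during the last week of treatment, each participant will undergo the food brunch task". In Appendix 1, the later visits (3 and 4) appear to fall under the obese-only heading. The repeat OGTT, the repeat CGM and the repeat eating questionnaires are each limited to obese participants in their own sections. No section says this of the food task.

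**The concern.** A before/after change in a group that is all treated contains the drug effect plus everything else that changed between the two sessions. Here that includes a second exposure to the same six foods, knowing that one is on an active drug, weekly calls with clinicians (plus two more in week 1), and regression to the mean. The declared main contrast cannot take any of this out.

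The comparison with lean participants, as the plan describes it, does not help. It asks whether treated participants end up closer to a level. If lean participants eat less at baseline, which the documents do not state, a fall in intake from any cause moves the obese group toward that level.

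What is at stake is the conclusion. The plan says the adolescent pilot data are meant to support funding and add to the literature, so an overstated effect would be carried forward.

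**Working it through.** **Inputs.** From Analyses and Statistical Considerations: 30 obese and 15 lean participants. That section states no alpha, power, dropout, SD of change in intake or effect size for intake; its effect sizes are for brain imaging. There is therefore no planned figure for this contrast to reproduce. Assumed here: two-sided 5% test, no dropout, effects in units of the SD of the change, equal SD of change in both groups. The documents give no repeat-test data for the task, so the size of the non-drug shift, s, is also an assumption.

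**Step 1: how often a non-drug shift alone is significant.** For a paired t test with n = 30 and zero drug effect, the statistic is noncentral t with 29 df and noncentrality s × √30. The critical value is 2.045.

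| s (SD of change) | s × √30 | Probability significant |
|---|---|---|
| 0 | 0 | 5.0% |
| 0.1 | 0.55 | 8.3% |
| 0.2 | 1.10 | 18.5% |
| 0.3 | 1.64 | 35.5% |
| 0.4 | 2.19 | 56.3% |

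**Step 2: can the planned interaction be estimated?** Write μ for lean before, α for obese minus lean at baseline, β for time and γ for the interaction.

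- Lean before = μ
- Obese before = μ + α
- Obese after = μ + α + β + γ
- Lean after = μ + β, only if lean participants repeat the task

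Without the last line there are three means for four parameters (rank 3 of 4). Only β + γ, the within-obese change, is identified. With it the rank is 4, and γ is the obese change minus the lean change.

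**Step 3: precision if lean participants repeat the task.**

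- Within-obese change: SE = 1/√30 = 0.183 SD of change.
- Obese change minus lean change: SE = √(1/30 + 1/15) = 0.316 SD of change.
- A t test of 30 against 15 reaches 80% power at a difference of about 0.91 SD, against 0.53 SD for the paired test.

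**Step 4: would agreement in direction rescue causal wording?** Take a rule that allows drug-effect wording when the paired test is significant and the difference in change has the same sign. In 400,000 simulated trials per setting, with zero drug effect and the same shift in both groups, the rule is met in about 15%, 27% and 37% of trials at s = 0.2, 0.3 and 0.4. It lowers the Step 1 error rates but does not come near 5%.

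**The case against.** The strongest reply is that the plan already contains the comparison. The status-by-time interaction is the obese change minus the lean change, and the task description, read literally, has every participant do the task twice. The flow chart survives only as a broken table, and no legible row shows who does the food task when. This stands in part. A reader might infer that lean participants are never retested; the documents do not establish that. They do conflict: the second task is timed to the last week of treatment, and lean participants have no treatment period.

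It does not remove the main point. Even with a lean repeat, the declared main question is the within-obese change. Untreated lean participants share neither the obese group's expectancy, nor its weekly calls, nor any regression to the mean specific to that group.

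Other limits are fair:

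- Filming is planned at both sessions and for both groups, and diet-recording training goes to everyone. Neither separates treated from untreated.
- The calls are for safety monitoring, and no diet is imposed, so their effect on intake may be small.
- Participants are not selected on the food task itself, so regression to the mean on that outcome may also be small.
- A reader might infer that any non-drug change favours the drug. Only a shift toward the lean level would; a rise in intake on repetition would mask a drug effect.
- The trial is Phase 2A, is partly described as a pilot, and shows openly that it has no control. That makes a single-arm design defensible. It does not make the causal wording of Aim 1 defensible.

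**Conclusion.** The concern holds for the claim, not for the choice of a single-arm design. The main contrast estimates change from baseline during open-label liraglutide treatment. It does not isolate the effect of liraglutide, and resemblance to lean participants after treatment does not show that the drug caused it.

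The 19% to 56% range rests on assumed shifts of 0.2 to 0.4 SD of change. It shows how sensitive the test is and is not evidence that such a shift will occur. Neither its size nor its direction can be taken from the documents.

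That the documents conflict on lean retesting rests on their text alone. That the interaction cannot be estimated follows only if lean participants do the task once.

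**What to change.** 1. **Restate the claim.** In the Trial Summary, the Statement of Purpose/Objectives and the analysis section, give the main result as change from baseline during liraglutide treatment. Call the lean participants a reference group rather than controls. This costs only wording and a weaker claim.

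2. **Reconcile Eating Behavior Assessments, the analysis model and Appendix 1.**
   - If lean participants repeat the task, define its timing for people with no treatment period. Report the interaction already planned beside the within-obese change, as supportive only: it addresses repetition but not expectancy, contact or regression to the mean. Payments at the flow chart's $50 per visit come to 15 × $50 = $750. The full cost is higher, because the visit also needs IV placement and blood sampling, metabolic-kitchen weighing and video scoring.
   - If they do not, remove the interaction for this outcome. Compare obese participants before and after with the single lean baseline, and say that the lean value comes from a first exposure.

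3. **Do not let agreement in direction restore drug-effect wording.** Step 4 shows why, and such a rule would contradict item 1.

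A concurrent untreated obese group would be needed to support the causal wording. Splitting the present 30 into 15 and 15 would give 80% power only for a difference of about 1.06 SD of change, so at this size restating the claim is the practical course.

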## **DATA MANAGEMENT AND RECORD KEEPING**

The principal investigator is required to prepare and maintain adequate and accurate case histories designed to record all observations and other data pertinent to the investigation on each individual treated in the investigation. Data that are derived from source documents and reported on the CRF must be consistent with the source documents or the discrepancies must be explained. OnCore will be the designated electronic data capture tool. All data should be entered onto OnCore within 1 week of study entry.

## **ADMINISTRATIVE AND REGULATORY**

### **Data safety and monitoring plan**

Authority for patient safety will reside exclusively with the Principal Investigator. She will ensure data quality and completeness. The PI has the authority to recommend that the study protocol be terminated, temporarily suspended, or amended.

The data safety monitor for this study will be [name], PhD. [name] is an Associate Professor in the department of Pediatrics (Pediatric Endocrinology) at Yale University School of Medicine. [name] is a licensed pediatric endocrinologist with over a decade of experience in conducting clinical trials in children and young adults with diabetes. [name] is very familiar with the requirements for data safety monitoring. She also has several ongoing protocols with the Yale Human Investigation Committee (HIC). [name] is not an investigator on the proposed study and would function as an independent monitor. [name] will evaluate all Adverse and Serious Adverse Events and will assist the PI in preparing and sending the pertinent expedited reports to the appropriate persons as outlined above. She will monitor the study quarterly and review all adverse event sheets completed during that period. She will assist the PI in making critical decisions regarding subject's continuation in the study for safety reasons. She will review the summary of all Adverse Events for this study, which will be reported annually to the Yale Human Investigation Committee (HIC) and the ADA.

### **Project Team Meetings**

Scheduled meetings will be held weekly and will include the Principal investigators and research staff involved with the conduct of the protocol.

During these meetings, the investigators will discuss:

1. Safety of protocol participants (adverse events and reporting)
2. Validity and integrity of the data (data completeness on CRFs and complete source documentation)
3. Enrollment rate relative to expectation of target accrual (eligible and ineligible participants)
4. Retention of participants, adherence to the protocol and protocol violations
5. Protocol amendments

## **CONFIDENTIALITY & SECURITY OF DATA**

Data will be entered into OnCore. De-identified data will then be downloaded in Excel format for statistical analysis, which will be done on a HIPAA compatible, password protected encrypted laptop computer. All data entry will be performed by the study personnel. All source documentation will be retained at the research clinic in locked cabinets in locked offices.

## APPENDIX 1: TRIAL FLOW CHART

Lean & Obese		Obese Only										
Visit 1 CSRU	Visit 2 CSRU	Screen Visit/CGM placement	Food Snack Task	Week 1	Weeks 2-3	Week 4	Weeks 5-7	Week 8	Weeks 9-11	Visit 3 CSRU	Visit 4 CSRU	
Date												
Compensation	\$50	\$50								\$50	\$50 + \$50 study completion bonus	
Phone Call			2 calls									
Side Effect Assessment												
OGTT												
Screen Labs												
Labs												
FCI & DEBQ												
PHQ-9												
CGM+BOOST, ASA 24 & App Food Record	Remove 14 days later									Remove 14 days later		

**APPENDIX 2: PATIENT HEALTH QUESITONNAIRE (PHQ-9)**

*Over the last 2 weeks, how often have you been bothered by any of the following problems?*

	Not at all	Several days	More than half the days	Nearly every day
1. Little interest or pleasure in doing things	0	1	2	3
2. Feeling down, depressed, or hopeless	0	1	2	3
3. Trouble falling or staying asleep, or sleeping too much	0	1	2	3
4. Feeling tired or having little energy	0	1	2	3
5. Poor appetite or overeating	0	1	2	3
6. Feeling bad about yourself – or that you are a failure or have let yourself or your family down	0	1	2	3
7. Trouble concentrating on things, such as reading the newspaper or watching television	0	1	2	3
8. Moving or speaking so slowly that other people could have noticed. Or the opposite – being so fidgety or restless that you have been moving around a lot more than usual	0	1	2	3
9. Thoughts that you would be better off dead, or of hurting yourself	0	1	2	3

Total Score	Depression Severity
1-4	Minimal depression
5-9	Mild depression
10-14	Moderate depression
15-19	Moderately severe depression
20-27	Severe depression

